5.3.1.1 Imputation rules

CTC grading for blood differentials is based on absolute values. However, this data may not be reported as absolute counts but rather as percentage of WBC.

If laboratory values are provided as '<X' (i.e., below limit of detection) or '>X', prior to conversion of laboratory values to SI unit, these numeric values are set to X.

The following rules will be applied to derive the WBC differential counts when only percentages are available for a xxx differential

$$\text{xxx count} = (\text{WBC count}) \times (\text{xxx \%value}/100)$$

Further derivation of laboratory parameters might be required for CTCAE grading. For instance, corrected calcium can be derived using the reported total calcium value and albumin at the same assessment using the following formula:

$$\text{Corrected Calcium (mg/dL)} = \text{Calcium (mg/dL)} - 0.8 [\text{Albumin (g/dL)} - 4]$$

In order to apply the above formula, albumin values in g/L will be converted to g/dL by multiplying by 0.1), calcium values in mmol/L will be converted to mg/dL by dividing by 0.2495. For calculation of laboratory CTC grades 0 and 1, the normal range for derived corrected calcium is set to the same limits (in mg/dL) as for calcium.

Table 5-3 CTC grades v5.0 for laboratory values in Novartis Oncology

Lab test (toxicity)	SI unit	Lab test (NCDS)	Normal ranges (Merck manual, July 2015) and conversion factors	CTC Grades ⁽¹⁾				
				0	1	2	3	4
Hematology								
WBC ↓ WBC (Leukocytosis)	10 ⁹ /L 10 ⁹ /L	WBC WBC	3.9 – 10.7 x 10 ⁹ /L	≥ LLN	< LLN - 3.0 x 10 ⁹ /L -	< 3.0 – 2.0 x 10 ⁹ /L -	< 2.0 – 1.0 x 10 ⁹ /L > 100 x 10 ⁹ /L	< 1.0 x 10 ⁹ /L -
Hemoglobin (Anemia) Hemoglobin ↑	g/L g/L	HGB HGB	120 - 160 g/L or 7.4 - 9.9 mmol/L (F) 140 - 170 g/L or 8.7 – 10.6 mmol/L (M) (16.113 x mmol/L = g/L)	≥ LLN	< LLN - 100 g/L < LLN - 6.2 mmol/L Increase >0-20 g/L above ULN	< 100 - 80 g/L < 6.2 - 4.9 mmol/L Increase >20-40 g/L above ULN	< 80 g/L < 4.9 mmol/L Increase >40 g/L above ULN	- -
Platelets ↓	10 ⁹ /L	PLAT	150 - 350 x 10 ⁹ /L	≥ LLN	< LLN - 75.0 x 10 ⁹ /L	< 75.0 - 50.0 x 10 ⁹ L	< 50.0 - 25.0 x 10 ⁹ /L	< 25.0 x 10 ⁹ /L
Neutrophils ↓	10 ⁹ /L	NEUT		≥2x10 ⁹ /L	< 2.0 - 1.5 x 10 ⁹ /L	< 1.5 - 1.0 x 10 ⁹ /L	< 1.0 - 0.5 x 10 ⁹ /L	< 0.5 x 10 ⁹ /L
Lymphocytes ↓ Lymphocytes ↑	10 ⁹ /L 10 ⁹ /L	LYM LYM		≥1.5x10 ⁹ /L	< 1.5 - 0.8 x 10 ⁹ /L -	< 0.8 - 0.5 x 10 ⁹ /L > 4 - 20 x 10 ⁹ /L	< 0.5 - 0.2 x 10 ⁹ /L > 20 x 10 ⁹ /L	< 0.2 x 10 ⁹ /L -
Biochemistry								
AST ↑	U/L	AST	0 - 35 U/L or 0 – 0.58 ukat/L (60 x ukat/L = U/L)	≤ ULN	> ULN – 3.0 x ULN	> 3.0 - 5.0 x ULN	> 5.0 - 20.0 x ULN	> 20.0 x ULN
ALT ↑	U/L	ALT	0 - 35 U/L or 0 – 0.58 ukat/L (60 x ukat/L = U/L)	≤ ULN	> ULN – 3.0 x ULN	> 3.0 - 5.0 x ULN	> 5.0 - 20.0 x ULN	> 20.0 x ULN
Total bilirubin ↑	umol/L	BILI	5.1 – 20.5 umol/L or 0.3 – 1.2 mg/dL (17.1 x mg/dL = umol/L)	≤ ULN	> ULN - 1.5 x ULN	> 1.5 - 3.0 x ULN	> 3.0 - 10.0 x ULN	> 10.0 x ULN
Alk. Phosphatase ↑	U/L	ALP	36 - 92 U/L or 0.5 - 1.5 ukat/L (60 x ukat/L = U/L)	≤ ULN	> ULN - 2.5 x ULN	> 2.5 - 5.0 x ULN	> 5.0 - 20.0 x ULN	> 20.0 x ULN
Creatinine ↑	umol/L	CREAT	61.9 - 115 umol/L or 0.7 – 1.3 mg/dL (88.4 x mg/dL = umol/L)	≤ ULN	> ULN - 1.5 x ULN	> 1.5 - 3.0 x ULN	> 3.0 - 6.0 x ULN	> 6.0 x ULN
Creatinine kinase ↑	U/L	CK	30 – 170 U/L or 0.5 – 2.83 ukat/L (60xukat/L=U/L)	≤ ULN	> ULN - 2.5 x ULN	> 2.5 - 5.0 x ULN	> 5.0 - 10.0 x ULN	> 10.0 x ULN

Final

Lab test (toxicity)	SI unit	Lab test (NCDS)	Normal ranges (Merck manual, July 2015) and conversion factors	CTC Grades ⁽¹⁾				
				0	1	2	3	4
Albumin (Hypoalbuminemia)	g/L	ALB	35 - 55 g/L or 3.5 to 5.5 g/dL	≥ LLN	< LLN - 30 g/L	< 30 - 20 g/L	< 20 g/L	-
Lipase ↑	U/L	LIPASE	<95 U/L or <1.58 ukat/L (60 x ukat/L = U/L)	≤ ULN	> ULN - 1.5 x ULN	> 1.5 - 2.0 x ULN	> 2.0 - 5.0 x ULN	> 5.0 x ULN
Amylase ↑	U/L	AMYLASE	0 - 130 U/L or 0 – 2.17 ukat/L (60 x ukat/L = U/L)	≤ ULN	> ULN - 1.5 x ULN	> 1.5 - 2.0 x ULN	> 2.0 - 5.0 x ULN	> 5.0 x ULN
Calcium (corrected) (Hypercalcemia)	mmol/L	CACALC	2.2 - 2.6 mmol/L or 9 - 10.5 mg/dL (0.2495 x mg/dL = mmol/L)	≤ ULN	> ULN - 11.5 mg/dL > ULN - 2.9 mmol/L	> 11.5 - 12.5 mg/dL > 2.9 - 3.1 mmol/L	> 12.5 - 13.5 mg/dL > 3.1 - 3.4 mmol/L	> 13.5 mg/dL > 3.4 mmol/L
Calcium (corrected) (Hypocalcemia)	mmol/L	CACALC		≥ LLN	< LLN - 8.0 mg/dL < LLN - 2.0 mmol/L	< 8.0 - 7.0 mg/dL < 2.0 - 1.75 mmol/L	< 7.0 - 6.0 mg/dL < 1.75 - 1.5 mmol/L	< 6.0 mg/dL < 1.5 mmol/L
Magnesium ⁽²⁾ (Hypermagnesemia)	mmol/L	MG	0.62 – 0.99 mmol/L or 1.5 – 2.4 mg/dL (0.4114 x mg/dL = mmol/L)	≤ ULN	> ULN - 3.0 mg/dL > ULN - 1.23 mmol/L	-	> 3.0 – 8.0 mg/dL > 1.23 – 3.3 mmol/L	> 8.0 mg/dL > 3.3 mmol/L
Magnesium ⁽²⁾ (Hypomagnesemia)	mmol/L	MG		≥ LLN	< LLN - 1.2 mg/dL < LLN - 0.5 mmol/L	< 1.2 - 0.9 mg/dL < 0.5 - 0.4 mmol/L	< 0.9 - 0.7 mg/dL < 0.4 - 0.3 mmol/L	< 0.7 mg/dL < 0.3 mmol/L
Glucose (Hypoglycemia)	mmol/L	GLUCSN/ GLUCSF		≥ LLN	< LLN - 55 mg/dL < LLN - 3.0 mmol/L	< 55 - 40 mg/dL < 3.0 - 2.2 mmol/L	< 40 - 30 mg/dL < 2.2 - 1.7 mmol/L	< 30 mg/dL < 1.7 mmol/L
Potassium (Hyperkalemia)	mmol/L	K	3.5 - 5.0 mmol/L (0.2558 x mg/dL = mEq/L = mmol/L)	≤ ULN	> ULN - 5.5 mmol/L	> 5.5 - 6.0 mmol/L	> 6.0 - 7.0 mmol/L	> 7.0 mmol/L
Potassium (Hypokalemia)	mmol/L	K		≥ LLN	< LLN - 3.0 mmol/L	-	< 3.0 - 2.5 mmol/L	< 2.5 mmol/L
Sodium (Hyponatremia)	mmol/L	SODIUM	136 - 145 mmol/L (0.435 x mg/dL = mEq/L = mmol/L)	≤ ULN	> ULN - 150 mmol/L	> 150 - 155 mmol/L	> 155 - 160 mmol/L	> 160 mmol/L
Sodium (Hyponatremia)	mmol/L	SODIUM		≥ LLN	< LLN - 130 mmol/L	-	< 130 - 120 mmol/L	< 120 mmol/L
Coagulation								
INR ↑	1	INR	0.8 – 1.2	≤ ULN	> ULN - 1.5 x ULN	> 1.5 - 2.5 x ULN	> 2.5 x ULN	-
Activated partial thromboplastin time ↑	sec	APTT	25 - 35 sec	≤ ULN	> ULN - 1.5 x ULN	> 1.5 - 2.5 x ULN	> 2.5 x ULN	-

Final

Lab test (toxicity)	SI unit	Lab test (NCDS)	Normal ranges (Merck manual, July 2015) and conversion factors	CTC Grades ⁽¹⁾				
				0	1	2	3	4
ULN = Upper Limit of Normal range; LLN = Lower Limit of Normal range LAB CTC grades 1, 2, 3, 4 overrule the study specific (central or local) normal range criteria , e.g., if ULN of Sodium is 151 mmol/L and the value is 151 mmol/L, CTC grade 2 is assigned although the value is ≤ ULN. Life-threatening consequences and/or hospitalization are not considered for determination of LAB CTC grades 3 and 4. Concomitant usage of anticoagulation therapy (for INR and Fibrinogen) is not considered either. Values and LNRs for blood differentials can be given as %, absolute values should then be calculated using WBC. Generally, ≥ 1.5 x 10⁹/L (lymphocytes) and ≥ 2 x 10⁹/L (neutrophils) are considered as LAB CTC grade 0 . For Creatinine and Fibrinogen, the comparison with baseline is not considered for derivation of LAB CTC grades.								

6 Reference

Brookmeyer R and Crowley J (1982) A Confidence Interval for the Median Survival Time. *Biometrics*; 38(1):29-41.

Clopper CJ and Pearson ES (1934) The use of confidence or fiducial limits illustrated in the case of the binomial. *Biometrika*; 26(4):404–13.

Klein JP and Moeschberger ML (1997) *Survival analysis: techniques for censored and truncated data*. Springer.

Kalbfleisch JD and Prentice RL (2002) *The Statistical Analysis of Failure Time Data*. Wiley Series in Probability and Statistics.

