Most of the reported adverse events (AEs) are mild or moderate in severity. The most frequent AEs suspected to be related to capmatinib of any grade reported in the largest single agent trial CINC280A2201 with 302 subjects were peripheral edema (40.4%), nausea (32.8%), increased blood creatinine (19.2%), vomiting (19.2%), decreased appetite (13.2%), fatigue (13.2%), and diarrhea (11.6%), with most of them being Grade 1/2.

The Grade 3/4 AEs suspected to be related to capmatinib in the CINC280A2201 study include peripheral edema (6.3%), increased lipase (5.0%), fatigue (3.3%), increased alanine aminotransferase (4.0%), vomiting (2.0%), nausea (1.7%), hypophosphataemia (1.7%), and increased aspartate aminotransferase (1.7%).

As of 28-Sep-2018, pneumonitis and interstitial lung disease (ILD) have been reported from both capmatinib single agent studies and combination studies with EGFR TKIs (Tyrosine kinase inhibitors), including events with fatal outcomes. In capmatinib single agent study CINC280A2201, 6 patients (2.0%) experienced suspected pneumonitis of any grade. Three patients (1.0%) experienced Grade 3/4 pneumonitis (1 with a fatal outcome) and two patients (0.7%) experienced Grade 3/4 interstitial lung disease and reported as suspected to be related to capmatinib treatment. All patients had multiple contributing factors including prior radiotherapy and prior therapy with checkpoint inhibitors, concurrent progressive disease of NSCLC. Careful monitoring of patients for signs and symptoms of pneumonitis in capmatinib studies is suggested, especially in combination studies with EGFR TKIs.

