The following will be reported:

- Summary of notable vital sign values

Table with descriptive statistics at baseline, one or several post-baseline time points and change from baseline to this/these post-baseline time points

12-lead ECG

- 12-lead ECGs including PR, QRS, QT, QTcF intervals and heart rate (HR) will be obtained for each subject during the study. ECG data will be read and interpreted locally.
- A listing of these subjects will be produced (by treatment arm).

Clinical laboratory evaluations

All laboratory data will be listed by treatment arm, subject, and visit/time and if normal ranges are available abnormalities will be flagged. Summary statistics will be provided by treatment and visit/time. Shift tables using the low/normal/high/ (low and high) classification will be used to compare baseline to the worst on-treatment value.

Grading of laboratory values will be assigned programmatically as per NCI Common Terminology Criteria for Adverse Events (CTCAE) version 5.0. The calculation of CTCAE grades will be based on the observed laboratory values only, clinical assessments will not be taken into account.

CTCAE Grade 0 will be assigned for all non-missing values not graded as 1 or higher. Grade 5 will not be used.

For laboratory tests where grades are not defined by CTCAE v5.0, results will be categorized as low/normal/high based on laboratory normal ranges.

The following summaries will be generated separately for hematology, and biochemistry tests:

- Listing of all laboratory data with values flagged to show the corresponding CTCAE v5.0 grades if applicable and the classifications relative to the laboratory normal ranges

For laboratory tests where grades are defined by CTCAE v5.0

- Worst post-baseline CTCAE grade (regardless of the baseline status). Each subject will be counted only once for the worst grade observed post-baseline.
- Shift tables using CTCAE v5.0 grades to compare baseline to the worst on-treatment value

For laboratory tests where grades are not defined by CTCAE v5.0,

- Shift tables using the low/normal/high/ (low and high) classification to compare baseline to the worst on-treatment value.

In addition to the above-mentioned tables and listings, other exploratory analyses, for example, figures plotting time course of raw or change in laboratory tests over time or box plots might be specified in the SAP.

Other safety evaluations

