2.8.4 Adverse events of special interest / grouping of AEs

An AESI is a grouping of AEs that are of scientific and medical concern specific to compound INC280. These groupings are defined using MedDRA terms, SMQs (standardized MedDRA queries), HLGs (high level group terms), HLTs (high level terms) and PTs (preferred terms).

Customized SMQs (Novartis MedDRA queries, NMQ) may also be used. A NMQ is a customized group of search terms which defines a medical concept for which there is no official SMQ available or the available SMQ does not completely fit the need. It may include a combination of single terms and/or an existing SMQ, narrow or broad. Pre-defined AESIs for the current study are as follows:

- Hepatotoxicity
- Central nervous system (CNS) toxicity
- Interstitial Lung Disease and Pneumonitis
- QTc interval prolongation
- Pancreatitis
- Drug-drug interactions with strong CYP3A4 inducers
- Teratogenicity
- Renal dysfunction
- Photosensitivity

For each specified AESI, number and percentage of subjects with at least one event of the AESI occurring during on-treatment period will be summarized.

Summaries of these AESIs will be provided by treatment arm (INC280 + PEMBRO and PEMBRO alone). A listing of all grouping levels down to the MedDRA PTs used to define each AESI will be generated.

Note: From the eCRS, only risk where “Core Safety Risk” = Y should be selected to report AESI in the CSR (the variable name in GPS, for “Core Safety Risk”, is “SP”).

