5.3 Laboratory parameters derivations

5.3.1 CTC grading for laboratory parameters

Grade categorization of lab values will be assigned programmatically as per NCI CTCAE version 5.0. The calculation of laboratory CTC grades will be based on the observed laboratory values only, clinical assessments will not be taken into account. The criteria to assign CTC grades are given in Novartis internal criteria for CTC grading of laboratory parameters (see [Table 5-3](#)). The latest available version of the document based on the underlying CTCAE version 5.0 at the time of analysis will be used.

For laboratory tests where grades are not defined by CTCAE version 5.0, results will be graded by the low/normal/high classifications based on laboratory normal ranges.

A severity grade of 0 will be assigned for all non-missing lab values not graded as 1 or higher. Grade 5 is not applicable. For laboratory tests that are graded for both low and high values, summaries will be done separately and labeled by direction, e.g., sodium will be summarized as hyponatremia and hypernatremia.

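### SAP Table 5-3 and section 2.8.5.2 leave a creatinine rise within the normal range out of the programmed laboratory tables, and the SAP does not list the protocol outputs that would show it

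*SAP*

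**What the plan says.** **Grading rule.** SAP 5.3.1 states: "Grade categorization of lab values will be assigned programmatically as per NCI CTCAE version 5.0". It adds: "A severity grade of 0 will be assigned for all non-missing lab values not graded as 1 or higher". In Table 5-3 every creatinine cut-off is a multiple of ULN: grade 0 up to 1, grade 1 up to 1.5, grade 2 up to 3, grade 3 up to 6, and grade 4 beyond. The table footnote begins "For Creatinine and Fibrinogen, the comparison with baseline is" and finishes by saying that this comparison is not used for the laboratory grades.

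**Outputs in the SAP.** For a graded biochemistry test such as creatinine, SAP 2.8.5.2 lists three: worst grade after baseline, a shift table of grade from baseline to worst on-treatment value, and a listing restricted to grades 3 and 4.

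**Outputs in the protocol.** Section 12.5.2 asks for these grade-based tables and for more. It says "Summary statistics will be provided by treatment and visit/time", and it calls for a listing of all laboratory data by arm, subject and visit. SAP section 4 says that the protocol's analyses were not changed.

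**Why creatinine is of interest.** Protocol 1.1.1 reports raised blood creatinine, suspected to be capmatinib-related, in 19.2% of the 302 subjects in the largest single-agent study. SAP 2.8.4 includes "Renal dysfunction" among the adverse events of special interest (AESIs). It says of the AESI categories: "These groupings are defined using MedDRA terms, SMQs (standardized MedDRA queries", followed by other MedDRA levels. Laboratory grades play no part in them.

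**The concern.** A drug effect on creatinine shows first as a change from the subject's own starting value. A scale anchored only at ULN cannot register that change until the value leaves the normal range. All three creatinine outputs in SAP 2.8.5.2 are built on that scale, so they share the same blind region. The two protocol outputs that would show the change, by-visit statistics and the full listing, are not among the outputs that the SAP itemises.

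At stake is how completely the clinical study report describes a recognised capmatinib effect. The study stopped enrolling because the combination was poorly tolerated, so the safety description is one of its main remaining products. Elsewhere the SAP does use change from baseline: the notable ECG criteria (2.8.6.1) and notable vital-sign criteria (Table 2-3) both include it. The creatinine tables have no counterpart.

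**Working it through.** **1. Reproduce the printed range.** Table 5-3 gives "61.9 - 115 umol/L or 0.7 – 1.3 mg/dL (88.4 x mg/dL = umol/L". With the stated factor, 0.7 × 88.4 = 61.88 and 1.3 × 88.4 = 114.92, which round to 61.9 and 115. The range is internally consistent and is used below as LLN and ULN.

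**2. Largest rise that stays grade 0.** Grade 0 means value ≤ ULN, so the largest fold-rise is ULN / baseline. Grade 2 starts above 1.5 × 115 = 172.5 umol/L, so the fold-rise needed to exceed grade 1 is 172.5 / baseline. Mid-range is (61.9 + 115)/2 = 88.45.

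| Baseline (umol/L) | Largest fold-rise at grade 0 | Fold-rise to pass grade 1 |
|---|---|---|
| 61.9 (LLN) | 115/61.9 = 1.86 | 172.5/61.9 = 2.79 |
| 65 | 1.77 | 2.65 |
| 70 | 1.64 | 2.46 |
| 75 | 1.53 | 2.30 |
| 88.45 (mid-range) | 1.30 | 1.95 |
| 115 (ULN) | 1.00 | 1.50 |

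A 1.5-fold rise stays grade 0 for any baseline up to 115/1.5 = 76.7 umol/L. A full doubling stays grade 0 only from 115/2 = 57.5 umol/L or below, which is under the printed LLN.

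**3. Reach of the listing.** Grade 3 starts above 3 × 115 = 345 umol/L. That is 345/61.9 = 5.57 times baseline from LLN and 345/88.45 = 3.90 times from mid-range.

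**4. Follow one subject through the outputs.** Take a baseline of 70 and a worst value of 112 umol/L. The ratio to baseline is 112/70 = 1.60, and 112/115 = 0.97 of ULN, so the grade is 0. The subject counts as grade 0 in the worst-grade table, as 0 to 0 in the shift table, and is absent from the listing.

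**5. Compare the two documents on laboratory outputs.**

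| Output | Protocol 12.5.2 | SAP 2.8.5.2 |
|---|---|---|
| Worst grade after baseline | yes | yes |
| Grade shift table | yes | yes |
| Summary statistics by treatment and visit/time | yes | not listed |
| Listing of all laboratory data | yes | grade 3 or 4 only |

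The last two rows apply to every laboratory parameter, not only creatinine. Neither is declared in SAP section 4.

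**6. Check that the data exist.** Protocol Table 8-2 schedules chemistry on day 1 of each cycle. Capmatinib was stopped after the halt of 21 January 2021. Capture of safety results in the eCRF ended with amendment 03, dated 21 April 2021 (protocol 8.4). The period on capmatinib should therefore be covered.

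**The case against.** The other side has several good points.

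- **The rule is disclosed and consistent.** Protocol Table 6-6 uses the same ULN-only creatinine grades, protocol 12.5.2 bases grades on observed laboratory values only, and the footnote says openly that baseline is left out. This stands: the grades should be kept, and no further footnote is needed.
- **Rises can be caught elsewhere.** Protocol 10.1.1 has clinically significant results identified partly through marked changes from baseline or the previous visit, and 8.4.1 has clinically significant abnormalities recorded as adverse events or medical history. A reader might infer that a within-range rise goes unrecorded altogether, or that the renal AESI count is too low. The documents support neither: adverse event and AESI counts come from reported, coded events that the footnote does not touch, and creatinine is not itself an AESI. That route depends on investigator judgement, so it does not replace a tabulation of the measured values.
- **The missing outputs may be planned.** SAP 2.1 promises descriptive statistics for quantitative safety measurements, SAP 2.1.1.5 mentions change-from-baseline summaries, and table shells exist in a separate document. This stands in part. The outputs may yet be produced, but the section that itemises laboratory outputs does not name them, and its listing is narrower than the protocol's.
- **No formal test depends on these tables, and capmatinib has been stopped.** True. It limits the consequence to the quality of the safety description.

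**Conclusion.** The point holds as a reporting gap with two parts. First, with the range in Table 5-3, a creatinine rise of up to 1.86-fold from LLN, or 1.30-fold from mid-range, is grade 0 and does not show in the laboratory tables that the SAP programmes. Second, SAP 2.8.5.2 lists neither the by-visit summary statistics nor the full laboratory listing of protocol 12.5.2, while SAP section 4 reports no change.

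The factors assume the printed range. Laboratories are local (protocol 8.4.1), so actual limits and factors will differ. The allowance approaches a doubling only at or very near LLN.

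Three stronger readings are not supported. A reader might infer that the difference between arms is understated; the same rule applies to both arms, and the documents give no creatinine data from which an effect on the comparison could be shown. A reader might infer that the grades are mislabelled as CTCAE v5.0; the footnote hints that a baseline criterion exists, but neither document sets it out. A reader might want the share of subjects affected; that depends on the baseline distribution, which the documents do not give.

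**What to change.** 1. Keep the ULN-based creatinine grades as they are.
2. In SAP 2.8.5.2, restore the protocol 12.5.2 summary statistics by treatment and visit/time and the listing of all laboratory data. If they are not to be produced, declare that in SAP section 4 with the reason.
3. Add one by-arm summary of each subject's worst on-treatment creatinine divided by baseline: median, range, and counts above descriptive thresholds such as 1.5, 2 and 3 times baseline. These thresholds are suggestions for description only; the documents give none, and they carry no implication for patient management.

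The cost is a few lines of SAP text, one new table and two outputs that the protocol already requires, all from data collected before amendment 03. The drawback is that the ratio table will also count reversible rises without renal injury, so it should be read beside the Renal dysfunction AESI and the BUN or urea results.
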